7 SAFETY REPORTING	11
7.1 Reporting of Adverse Drug Reactions	11
8 CENTRAL REVIEW	11
8.1 Endpoint Adjudication	11
9 STATISTICAL CONSIDERATIONS	12
9.1 Sample Size	12
9.2 Statistical Analysis	12
9.3 Interim Analyses	12
10 STUDY ORGANIZATION and COMMITTEES	13
10.1 Study Coordination	13
10.2 Trial Executive Committee	13
10.3 Trial Management Committee	13
10.4 Independent Safety and Data Monitoring Committee	13
11 ADMINISTRATIVE ASPECTS	13
11.1 Ethics and Regulatory Compliance	13
11.2 Confidentiality	14
11.3 Protocol Amendments	14
11.4 Data Handling and Record Keeping	14
11.5 Monitoring, Audit and Inspection	15
11.6 Clinical Study Report	15
11.7 Publication Policy	15
12 PROTOCOL AMENDMENTS	15
13 REFERENCES	16
14 APPENDICES	17
14.1 Appendix 1. Questionnaire to Patients	17

SYNOPSIS

Background	
This observational study will follow participants who completed follow-up in the FOURIER OUTCOMES trial to evaluate the long-term effects of evolocumab treatment. Long-term post-trial (legacy) beneficial effects have been reported with statins, niacin, hypoglycemic therapy and fibrates. Whether similar effects are seen after LDL cholesterol (LDL-c) lowering by PCSK9 inhibition is currently unknown. Evolocumab therapy causes a profound reduction in LDL cholesterol of approximately 60%. Statins have shown legacy effects over 5 years post-trial, including a 7% reduction in total mortality in meta-analysis and 12% reduction in coronary mortality. It would therefore be hypothesized that additional effects beyond the trial period would be conferred by previous evolocumab treatment. It is also important to assess the long-term safety of prior evolocumab treatment.

Aim	
To evaluate potential long-term effects on cardiovascular outcomes of evolocumab treatment in participants who have completed follow-up in the FOURIER OUTCOMES trial.

Primary objective	
1. To evaluate the potential long-term effect of evolocumab treatment on a composite of CV death, MI, stroke or coronary revascularization in patients completing participation in the FOURIER OUTCOMES trial.
Secondary objectives	
2. To evaluate the long-term effect of evolocumab treatment on CV death, MI and stroke.3. To evaluate the long-term effect of evolocumab treatment on CV death.4. To evaluate the long-term effects of evolocumab treatment on CHD death.5. To evaluate the long-term effect of evolocumab treatment on the individual components of the primary endpoint and any other CV hospitalizations.6. To evaluate the long-term effect of evolocumab treatment on amputations and peripheral revascularization.7. To evaluate the long-term effect of evolocumab treatment in terms of all-cause death (and non-CV, including cancer, death).
Exploratory objective	
8. To assess the effect of use of lipid-lowering treatment classes (statins, cholesterol absorption inhibitors, PCSK9i).9. To assess the effect modification by baseline characteristics on defined study outcomes above.
Design	
International multi-center observational, longitudinal follow-up study of participants who participated in the FOURIER OUTCOMES trial.

Population	
Participants in selected countries who completed the FOURIER OUTCOMES trial.

Study treatments	
None.

Assessments	
Participants will be remotely assessed (via questionnaire) upon entry into the FOURIER LEGACY study, approximately 6 and 12 months later and

[figure not shown]
then approximately annually to obtain a total of 5 years' follow-up after the date of last contact in the FOURIER OUTCOMES trial to collect details of cardiovascular hospitalizations, mortality and lipid-lowering therapy classes.

Statistical considerations

A minimum of 10,000 participants, followed over 5 years post-trial, with an assumed average post-trial event rate of 5% per annum for the primary endpoint, would have over 95% power at $2P=0.05$ to detect a 20% proportional event reduction accruing post-trial. It will also offer 80% power at $2P=0.05$ to detect a 23% reduction in CVD (from 4.94% to 3.8%).

Interim analyses of accrued data may be conducted annually post-trial as agreed from time to time by the study Steering Committee and funder. Analyses will be by intention-to-treat based on original allocated treatment in the parent FOURIER OUTCOMES trial.

Study Schema

1 BACKGROUND

On-going and additional clinical benefits of statin therapy after trial completion have been demonstrated to accrue from a number of trials (including the 4S Study¹ and the LIPID Study^{2,3} in secondary prevention patients, and the WOSCOPS Study^{4,5} and ASCOT study⁶ in primary prevention). Furthermore, collectively in all those trials contributing to the Cholesterol Treatment Trialists' Collaboration⁷ with accessible published follow-up data, in patients who received active treatment rather than placebo over (the 3–6 years of) the original trial period, the same pattern of on-going advantage and additional risk reduction is seen.⁸ This is seen despite mostly identical usage rates of lipid-lowering therapy between the original groups for many years after completion of the trials.

In meta-analysis of the trials with accessible published post-trial data, an 8% additional reduction in total mortality at 2 years after trial close, 18% reduction in coronary mortality, and 7% reduction in total mortality and 12% reduction in coronary mortality over the next 5 years after trial close was recently reported.⁸ Collectively, these findings could have a major impact on how early initiation of lipid-lowering treatment should be considered in patients at risk. Also, because of greater emerging absolute risk differences than those apparent immediately at trial end, the net clinical benefits estimated relative to treatment costs becomes more favorable for earlier (vs deferred) intervention attributable to the original treatment assignment.

The same may or may not be true of PCSK9 inhibitor therapy, and so this needs to be examined prospectively and systematically. Similarly, in terms of potential safety issues, longer-term data after exposure provides more reliable evidence about the safety of therapy intended to be used for many years.

The FOURIER OUTCOMES trial was a randomized double-blind placebo-controlled trial that demonstrated significant clinical benefits, with a 15% reduction in the composite endpoint of CVD death, MI, stroke, UAP or urgent revascularization over a median of 2.2 years follow-up, and a 20% reduction in CVD death, MI, and stroke, with no excess of any important adverse events.^{9,10} However, while beneficial over just a few years, these treatments will be designed for long-term use, such that high confidence in the value of the therapy can be better established with longer-term efficacy and safety data related to the treatment received during the FOURIER OUTCOMES trial.

The ODYSSEY OUTCOMES trial showed that among patients who had a previous acute coronary syndrome (ACS) and who were receiving high-intensity statin therapy, the risk of recurrent ischemic cardiovascular events was lower among those who received alirocumab than among those who received placebo.¹¹

We hypothesize that, in this observational study of participants who had taken part in the FOURIER OUTCOMES trial, prior use of evolocumab compared with placebo during the randomized FOURIER OUTCOMES trial, irrespective of post-trial treatment with or without further evolocumab, will confer additional effects post-trial on cardiovascular events and mortality beyond those observed at the end of the randomized study period; and that this will occur without any adverse signal on non-cardiovascular mortality.

2 AIM AND OBJECTIVES

The aim of this study is to determine potential long-term effects on cardiovascular outcomes of evolocumab treatment in patients enrolled in the FOURIER OUTCOMES trial through extended follow-up of selected participants beyond the treatment period.

The **primary objective** is to evaluate potential long-term effects of evolocumab treatment on a composite of CV death, MI, stroke or coronary revascularization in patients completing participation in the FOURIER OUTCOMES trial over a period of up to 5 years following completion of the FOURIER OUTCOMES trial.

The **secondary objectives**, each over a period of up to 5 years following completion of the FOURIER OUTCOMES trial, are:

1. To evaluate the long-term effect of evolocumab treatment on CV death, MI and stroke.
2. To evaluate the long-term effect of evolocumab treatment on CV death.
3. To evaluate the long-term effect of evolocumab on CHD death.
4. To evaluate the long-term effect of evolocumab treatment on the individual components of the primary endpoint and any other cardiovascular hospitalizations.
5. To evaluate the long-term effect of evolocumab treatment on amputation and peripheral revascularization.
6. To evaluate the long-term effect of evolocumab treatment in terms of all-cause death (and non-CV, including cancer, death).

Two exploratory analyses will be performed:

1. To assess effect modification of use of prescription lipid-lowering treatment classes (statins, cholesterol absorption inhibitors, PCSK9i) administered at FOURIER OUTCOMES trial entry on the outcomes above.
2. To assess the effect modification by baseline characteristics on defined study outcomes above.

3 DESIGN

International multi-center, longitudinal observational study of selected participants who completed the FOURIER OUTCOMES trial.

3.1 Target Population

Participants in selected countries who completed the FOURIER OUTCOMES trial, irrespective of non-fatal on-study events during FOURIER OUTCOMES trial, and who agree to take part in the FOURIER LEGACY study following study completion will be enrolled into this trial.

3.2 Study Enrolment

Subjects who completed the FOURIER OUTCOMES trial (defined as attendance at close-out visit irrespective of treatment compliance) will be approached by FOURIER OUTCOMES site investigators and asked about their interest in taking part in this trial. Contact details of those interested in taking part will be forwarded to the national co-ordinating center (NCC), who will contact participants to confirm consent.

Assent: Confirmation by site staff of the participant's agreement to be contacted for consent by the NCC will be provided to the NCC.

Consent: Participation will require a specific consent by each participant to allow on-going contact to be made periodically to achieve follow-up for a total of approximately 5 years from completion of the FOURIER OUTCOMES trial. Telephone consent may be acceptable if allowed by local

regulations and approved by the Ethics Committee. Additionally, approval to hold each participant's contact details (in addition to contact details for at least one relative not living with the participant) and details of treating physician(s) will be sought to facilitate reliable on-going follow-up, and signed authorization for study staff to seek supplementary information and source documentation about health events will be collected. Participants will provide details of the preferred mode of communication (SMS, email, letter, phone) at the time of consent. Personal data identifying trial participants will be held securely solely at each NCC for the purpose of follow-up.

3.2.1 Informed consent

Informed consent must be signed and dated by the participant, and signed and dated by the investigator, prior to registration and participation in the study.

3.2.2 Registration

Registration will be done according to the instructions in the Study Manual. Once the registration process has been completed, the participant will be identified using their original FOURIER OUTCOMES patient ID. Individuals may only be registered once in this trial.

4 TREATMENT PLAN

This is a purely observational study, and as such there are no study treatments. Participants remain under the care of their treating physician.

4.1 Concomitant Medication Reporting

Use of concomitant medications is solely at the discretion of participants and their treating physicians, including any lipid-modifying medication (including PCSK9 inhibitors). Use of lipid-modifying therapy classes will be recorded.

5 ASSESSMENT PLAN

5.1 Schedule of Assessments

	Study entry, 6 and 12 months later and then annually to a total of 5 years post-end of FOURIER OUTCOMES trial
MI	X
Stroke	X
Coronary revascularization	X
Other CV hospitalization	X
CV death	X
CHD death	X
Amputation/peripheral revascularization	X
Non-CV death	X
Lipid-lowering therapies	X
Any adverse drug reactions from evolocumab treatment	X

5.2 Details of Assessments

Participants will be contacted upon entry into the FOURIER LEGACY study, and then approximately 6 months later. Following this, contact will be made approximately annually to obtain follow-up for a total of 5 years after the date of last contact in the FOURIER OUTCOMES trial. Each participant will be sent a unique link to a secure website and asked to provide details of any cardiovascular events and lipid-lowering therapy classes used since the last contact (Appendix 1 lists data to be collected). A proportion of events will be adjudicated as detailed in Section 8.1.

Participants will be contacted directly (by their preferred method of communication) or via a proxy, as agreed and in accordance with local regulations.

Participants who do not complete the required information despite reminders will be contacted directly by the relevant NCC.

Where permitted by local regulations, permission will be sought to collect data from any available national/local registries.

All consenting participants are expected to be followed up to the end of the study. All efforts must be made to maintain follow-up per the visit schedule. If this is not possible, follow-up should still occur wherever possible via periodic contact, the participant's other nominated contacts, their usual doctors, contact at study closure and any available national/local registries, as permitted by local regulations.

To ensure no bias is introduced into the assessment of possible late safety signals from prior evolocumab treatment in the FOURIER OUTCOMES trial, every effort will be made to ascertain causes of death for participants who may have died since the FOURIER OUTCOMES trial close-out and prior to the commencement of this study.

5.3 *Withdrawal From Contact or From Follow-up*

Withdrawal from on-going contact by the designated NCC may occur at any time by participant request, with confirmation to be documented clearly. Withdrawal of consent should only occur if the participant refuses any further assessments or contact whatsoever. Any data collected prior to a participant's withdrawal of consent will be maintained in the database and analyzed.

It is expected that all options for continued participation are explained to the participant and the reason for refusal is documented.

For participants who formally withdraw consent from the study, direct ascertainment of health status at the end of the study or vital status via public records will be performed in compliance with local privacy laws/practices. If specifically requested, in accordance with local regulations, participant data can be removed completely.

6 OUTCOMES, ENDPOINTS AND OTHER MEASUREMENTS

6.1 *Cardiovascular Outcomes*

Wherever possible the definitions applied in the FOURIER OUTCOMES trial will be used in this study.

- Myocardial infarction is defined as presence of cardiac symptoms consistent with an ACS plus elevated cardiac biomarkers (e.g., elevated troponin); ECG changes consistent with myocardial ischemia or infarction (e.g., ST segment changes) can be used to support or confirm the diagnosis.
- Stroke is defined as any neurological dysfunction caused by brain, spinal cord, or retinal vascular injury as a result of hemorrhage or infarction or a focal neurologic deficit that persists for >24 hours without other obvious cause.
- Coronary revascularization is defined as any procedure intended to restore coronary blood flow either percutaneously (including angioplasty and stenting) or via coronary artery bypass surgery.

6.2 *Cardiovascular Death and Coronary Heart Death*

Cardiovascular death is defined as one of the following: death due to MI, stroke, heart failure, or other cardiovascular causes. Coronary heart death is defined as death due to acute MI or sudden cardiac death.

6.3 Non-cardiovascular Death

Non-cardiovascular death is defined as death from any non-cardiovascular cause.

6.4 Cardiovascular Hospitalization

Cardiovascular hospitalization is defined as hospitalization for any cardiovascular reason.

6.5 Amputation and Peripheral Revascularization

Amputation is defined as non-traumatic amputation of an extremity more proximal than the distal phalanx.

Peripheral revascularization is defined as revascularization of any peripheral artery either surgically or percutaneously.

6.6 Prescription Lipid-lowering Treatment Use

Use of prescription lipid-lowering treatment classes during follow-up period.

7 SAFETY REPORTING

7.1 Reporting of Serious Adverse Events (including SUSARs)

No information for adverse events on specific drugs will be collected in this trial for the following reasons:

- Extensive safety data for evolocumab was already gathered in a rigorous, double-blind, placebo-controlled manner in a very large number of individuals in the FOURIER OUTCOMES trial.
- Amgen, the maker of evolocumab, is conducting two open-label extension studies of evolocumab in 6700 patients who received evolocumab in FOURIER OUTCOMES trial, thereby extending the duration of exposure to evolocumab to 7 years. (ClinicalTrials.gov Identifiers: NCT02867813 and NCT03080935).

Participants will be under the clinical care of their primary physician with no care provided by the NCC. If the investigator suspects or becomes aware of an adverse drug reaction(s) (serious or non-serious) or product complaints related to evolocumab use (past or current), this information shall be reported to Amgen within one (1) business day of the investigators' awareness or to the concerned competent authority via the national spontaneous reporting system. If it is not known what PCSK9i inhibitor a subject was on at the time of the event, this information will still be reported.

8 CENTRAL REVIEW

8.1 Endpoint Adjudication

Event information (masked to previous FOURIER OUTCOMES trial treatment allocation) will be adjudicated centrally by each RCC. At least 10% of non-fatal CV events and all deaths will be selected for central adjudication by RCCs, and NCCs will be asked to collect source data for these events.

Further details of outcome definitions for adjudication can be found in the adjudication guidelines which will be based on definitions used in the FOURIER OUTCOMES trial endpoint committee charter.

9 STATISTICAL CONSIDERATIONS

9.1 Sample Size

The event rate for the primary endpoint in the parent FOURIER OUTCOMES trial among participants allocated to placebo was 11.3% over a median follow-up of 2.2 years (i.e., 5% per annum). For a minimum of 10,000 participants, followed over 5 years post-trial, with an assumed average post-trial event rate of 5% per annum for the primary endpoint excluding hospitalization for unstable angina pectoris (UAP), then the observational FOURIER LEGACY study would have over 95% power at $2P=0.05$ to detect an additional 20% proportional event reduction accruing post-trial, and over 90% power to detect an additional 15% proportional event reduction. The study would also offer 80% power at $2P=0.05$ to detect a 23% reduction in CVD death from 4.94% to 3.8% over up to 5 years.

9.2 Statistical Analysis

The analyses will examine the effects of long-term evolocumab therapy on cardiovascular events, total mortality, and cause-specific mortality. Analyses will include all participants who entered the FOURIER LEGACY study in participating countries, irrespective of whether they completed the FOURIER LEGACY study. (Data including baseline characteristics, medications, event history and during follow-up etc. will be incorporated into the follow-up database from the FOURIER OUTCOMES trial database). The characteristics of participants at participating sites/countries who did and did not contribute to the FOURIER LEGACY study will be compared. Likewise, the characteristics of subjects who complete the FOURIER LEGACY study vs. those who do not will be compared.

Qualitative and quantitative data will be described using counts, means, medians, and percentages with ranges or standard deviations as appropriate. Event data will be analyzed according to the participants' original randomly assigned therapy in the OUTCOMES study, on an intention-to-treat basis. Time to event information will be presented using Kaplan-Meier curves, and described according to Cox proportional hazard ratios (and 95% CIs), with comparisons between curves using standard log-rank tests. Similar methodology will be used for analyses of any pre-specified subgroups (e.g., baseline participant characteristics). In the circumstance that the hazards violate the test of proportionality, methods such as time-partitioned regression techniques will be utilized. Tests for interaction will be used to evaluate for evidence of differences in treatment effects between subgroups. Recurrent event analysis will be performed using the methods of Wei, Lin and Weissfeld¹². Analyses, both unadjusted and adjusted for baseline measures, will be performed. Cause-specific mortality will also be analyzed using competing risks methods.

Further analysis investigating the impact of baseline characteristics (at time of randomization into the OUTCOMES study) on events will be performed using regression methods (linear, logistic, and proportional hazards) as appropriate.

Separate analyses examining effects post study close will be performed to evaluate the trajectory of effects long-term using appropriate methods (e.g., landmark analysis and conditional probability plots), again by original treatment assignment, among the FOURIER LEGACY study cohort from the time of randomization.

No adjustments will be made for multiple comparisons. Statistical inferences will be drawn based on the 5% level of significance. Expanded details will be provided in a separate Statistical Analysis Plan prepared prior to interim analysis.

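### Deaths between parent-trial close-out and LEGACY entry fall inside the five-year window and are to be ascertained, but the Section 9.2 analysis set excludes them

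*Protocol*

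**What the plan says.** Section 9.2 of the protocol fixes the analysis set: "Analyses will include all participants who entered the FOURIER LEGACY study in participating countries, irrespective of whether they completed the FOURIER LEGACY study". It analyses events by original allocation "on an intention-to-treat basis". The trajectory and landmark analyses start at randomisation but again use only the LEGACY cohort.

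Entry has two conditions. Under Section 3.2 the person must have completed the parent trial, "defined as attendance at close-out visit irrespective of treatment compliance". Under Section 3.2.1, before registration, "Informed consent must be signed and dated by the participant".

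Section 2 sets every objective over up to five years from completion of the parent trial, and Section 5.2 runs follow-up from the last parent-trial contact. Section 5.2 also promises every effort to ascertain "causes of death for participants who may have died since the FOURIER OUTCOMES trial close-out and prior to the commencement of this study". Its stated reason is: "To ensure no bias is introduced into the assessment of possible late safety signals from prior evolocumab treatment".

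The one safeguard in Section 9.2 aimed at selection into LEGACY is a comparison of the characteristics of those who did and did not contribute.

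**The concern.** The outcome clock starts at parent close-out, but membership of the analysed cohort is decided later, at consent, and only living people can consent. Nobody in the cohort can have died in the interval. The protocol sees this risk in Section 5.2 and arranges to collect the missing deaths, yet Section 9.2 gives them no place in any analysis.

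All-cause, CV, CHD and non-CV death are affected directly. The primary composite is affected in part. The entry questionnaire asks about events since last contact, so survivors' non-fatal events in the gap are counted while fatal events in the same months are not. In analyses run from randomisation, cohort members are alive by selection for the whole parent trial as well. At stake are the number of deaths, the power for CVD death, the accuracy of absolute risks and Kaplan-Meier curves, and possibly the treatment comparison.

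**Working it through.** **Inputs.** From Section 9.1: at least 10,000 participants; CVD death 4.94% versus 3.8% over up to five years; 80% power at two-sided 0.05; primary endpoint 5% per annum with over 90% power for a 15% reduction. Assumed, because not stated: 1:1 allocation (5,000 per arm), constant hazards, the same gap g for everyone, and 10,000 people alive at entry.

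**Step 1: reproduce the plan's figure.** Power = Φ{[|p1 − p2| − 1.96·√(2p̄(1 − p̄)/n)] / √[p1(1 − p1)/n + p2(1 − p2)/n]}. With p1 = 0.0494, p2 = 0.038, p̄ = 0.0437 and n = 5,000: (0.0114 − 0.00801)/0.00409 = 0.829, so power is 79.6%. Expected deaths are 5,000 × (0.0494 + 0.038) = 437. The stated 80% is reproduced, but only if deaths count over the full five years.

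**Step 2: remove the gap.** Hazards are −ln(1 − 0.0494)/5 = 0.01013 and −ln(1 − 0.038)/5 = 0.00775 per year. Entrants can contribute deaths only over 5 − g years, so the proportions become 1 − exp[−hazard × (5 − g)].

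| Gap (years, assumed) | CVD deaths observable | Deaths lost | Power, CVD death | Power, primary, 15% reduction, if all endpoints are counted only from entry |
|---|---|---|---|---|
| 0 | 437 | 0 | 79.6% | 95.7% |
| 0.5 | 394 | 43 (10%) | 75.4% | 94.0% |
| 1 | 351 | 86 (20%) | 70.5% | 91.5% |
| 1.5 | 308 | 129 (30%) | 64.8% | 88.0% |
| 2 | 265 | 172 (39%) | 58.3% | 83.1% |

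**Step 3: absolute risks.** With a two-year gap and no delayed entry, a curve drawn from close-out would show five-year CVD death of 2.99% and 2.30% instead of 4.94% and 3.80%. The difference shrinks from 1.14 to about 0.70 percentage points. The ratio hardly moves: 2.30/2.99 = 0.77, as does 3.80/4.94.

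**Step 4: the hazard ratio.** If it is constant and the gap is unrelated to arm, it is essentially unchanged. A simulation at these hazards, with gaps uniform over one to three years, gave 0.7610 without delayed entry and 0.7612 with it. It shifts if the effect differs in the gap. With a one-year gap, 0.60 in the gap and 0.85 afterwards averages (0.60 × 1 + 0.85 × 4)/5 = 0.80, while entrants show 0.85. Reversing the two values gives (0.85 × 1 + 0.60 × 4)/5 = 0.65 against 0.60, so the shift can go either way.

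**Step 5: length of the gap.** No close-out or entry dates are given. The reference list cites the parent results as published in 2017, and the first listed amendment is dated April 2019. This suggests a gap that is not trivial but does not measure it.

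**The case against.** Several points against the concern stand.

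- A reader might infer classical immortal-time bias in the hazard ratio. The documents do not support that: both arms are conditioned on survival in the same way, and Step 4 shows almost no change when the gap is unrelated to arm and the ratio is constant.
- A reader might use the Background, which reports "an 8% additional reduction in total mortality at 2 years after trial close, 18% reduction in coronary mortality" and 12% over five years, to argue that entrants would show (0.88 × 5 − 0.82 × 2)/3 = 0.92 instead of 0.88. The same paragraph gives 8% and 7% for total mortality, and the same formula yields (0.93 × 5 − 0.92 × 2)/3 = 0.937 against 0.93, which is negligible. These are statin figures without confidence intervals, and the subtraction needs constant hazards and a cumulative five-year figure.
- Delayed entry for every endpoint would discard non-fatal gap events that the plan collects. With a two-year gap, power for a 15% reduction in the primary endpoint would be 83%, below the stated 90%.
- Section 9.2 does plan analyses adjusted for baseline measures. These can address measured imbalance between arms among entrants, but they cannot restore deaths that are outside the set.
- The missing deaths are not guaranteed to be available. Section 5.2 covers deaths before study commencement, not before each person's consent, and promises effort only.

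It can also be said that Section 5.2 collects these deaths only for late safety signals and that a separate SAP may add a mortality set. But late safety signals include mortality, and the Section 9.2 sentence would still need to be reconciled with any such set.

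**Conclusion.** The point holds as a conflict between Sections 9.2 and 5.2, and it should be fixed. Followed as written, Section 9.2 drops pre-entry deaths from every mortality analysis although they fall within the objectives' window. About 86 of 437 expected CVD deaths (20%) are lost per year of gap, and power falls from about 80% to 75%, 71% and 58% with gaps of 0.5, 1 and 2 years. These figures rest on 1:1 allocation, constant hazards, a common gap and exactly 10,000 entrants. The protocol gives 10,000 as a minimum, so a larger cohort would offset part of the loss of power.

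Absolute rates and Kaplan-Meier curves would be too favourable in both arms unless delayed entry is used. A biased hazard ratio is possible but not shown: it needs an effect that differs in the gap, or survival or participation that differs by arm, and the documents do not determine the direction. The intention-to-treat label is too strong for a cohort selected after randomisation by survival and consent.

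**What to change.** Amend Section 9.2, with matching text in Section 5.2, before any interim analysis:

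1. For all-cause, CV, CHD and non-CV death, pre-specify an analysis by randomised arm of all parent close-out attendees at participating sites or countries. Include the pre-entry deaths where local rules permit. Extend Section 5.2 from deaths before study commencement to deaths up to each person's consent.
2. In entrant-only mortality analyses and curves, including those run from randomisation, use delayed entry at the LEGACY entry date. For the primary composite use delayed entry only as a sensitivity analysis, so that non-fatal gap events are kept.
3. Tabulate participation and pre-entry deaths by randomised arm. For the entrant cohort, replace the intention-to-treat label with: by randomised arm among LEGACY entrants.

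The cost is mainly wording and modest programming. The real burden is vital status of close-out attendees who did not enter: it may be incomplete and depends on local rules, so its completeness must be reported by arm. Weighting for participation is optional.
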